3.0 PATIENT SELECTION

3.1 Inclusion Criteria

1. Histologically or cytologically confirmed squamous or non-squamous non-small cell lung cancer. Patients with known EGFR or ALK mutations are eligible only if they have received at least one line of targeted therapy for these mutations.

2. Availability of archival biopsy tissue or willingness to undergo a “baseline” biopsy prior to initiation of the trial for biomarker analysis, including PD-L1 by IHC.

Note: Results of PD-L1 testing are not required for enrollment.

3. Measurable disease defined as lesions that can be accurately measured in at least one dimension (longest diameter to be recorded) as ≥ 10 mm with CT scan, as ≥ 20 mm by chest x-ray, or ≥ 10 mm with calipers by clinical exam.
4. Prior use of an immune checkpoint blocker alone or in combination therapy.
5. At least 18 years of age.
6. ECOG performance status ≤ 1 (see Appendix A)
7. Normal bone marrow and organ function as defined below:
 - a. Absolute neutrophil count $\geq 1,500$ /cumm
 - b. Platelets $\geq 100,000$ /cumm
 - c. Hemoglobin ≥ 9.0 g/dL
 - d. Total bilirubin ≤ 1.5 x ULN
 - e. AST(SGOT)/ALT(SGPT) ≤ 3.0 x ULN or 5.0 x ULN in the setting of liver metastasis
 - f. Serum creatinine ≤ 1.5 x ULN or CrCl ≥ 40 mL/min. if serum creatinine is >1.5 times the ULN, a 24-hour urine collection to calculate creatinine clearance must be performed
8. Adequate coagulation function as defined by:
 - a. INR ≤ 1.5
 - b. PTT/aPTT < 1.5 x ULN

Note: Patients on full-dose anticoagulation must be on a stable dose (minimum duration 14 days) of oral anticoagulant or low molecular weight heparin (LMWH). If receiving warfarin, the patient must have an INR ≤ 3.0 . For heparin and LMWH there should be no active bleeding (that is, no bleeding within 14 days prior to first dose of protocol therapy) or pathological condition present that carries a high risk of bleeding (for example, tumor involving major vessels or known varices).

9. Urinary protein $\leq 1+$ on dipstick or routine urinalysis; if urine dipstick or routine analysis is $\geq 2+$, a 24-hour urine collection for protein must demonstrate < 1 g of protein in 24 hours to allow participation

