3.2 Exclusion Criteria

1. Treatment with cyclophosphamide, azathioprine, methotrexate, thalidomide, and anti-tumor necrosis factor [anti-TNF] agents) within 2 weeks prior to Cycle 1, Day 1.

Note: Patients who have received acute, low-dose, systemic immunosuppressant medications (e.g., a one-time dose of dexamethasone for nausea or premedication for contrast dye allergy) are eligible. The use of inhaled corticosteroids for chronic obstructive pulmonary disease (COPD) and mineralocorticoids (e.g., fludrocortisone) for patients with orthostatic hypotension or adrenocortical insufficiency is allowed.

2. A history of other malignancy ≤ 3 years previous with the exception of patients with a negligible risk of metastasis or death and with expected curative outcome (such as adequately treated carcinoma in situ of the cervix, basal or squamous cell skin cancer, localized prostate cancer treated surgically with curative intent, or ductal carcinoma in situ treated surgically with curative intent) or undergoing active surveillance per SOC management (e.g., Rai Stage 0 chronic lymphocytic leukemia, prostate cancer with Gleason score ≤ 6 and prostate-specific antigen (PSA ≤ 10 ng/mL, etc.).
3. Currently receiving any other investigational agents.
4. Symptomatic or untreated asymptomatic brain metastases. Patients with treated brain metastases are eligible if they are clinically stable with regard to neurologic function, off steroids after cranial irradiation (whole brain radiation therapy, focal radiation therapy, and stereotactic radiosurgery) ending at least 2 weeks prior to randomization, or after surgical resection performed at least 28 days prior to randomization. The patient may have no evidence of Grade ≥ 1 CNS hemorrhage based on pretreatment MRI or IV contrast CT scan (performed within 21 days before randomization).
5. A history of allergic reactions attributed to compounds of similar chemical or biologic composition to atezolizumab, ramucirumab, any other immune checkpoint blockade, chimeric or humanized antibodies, fusion proteins, or other agents used in the study.
6. Receiving chronic antiplatelet therapy, including aspirin, nonsteroidal anti-inflammatory drugs (NSAIDs, including ibuprofen, naproxen, and others), dipyridamole or clopidogrel, or similar agents. Once-daily aspirin use (maximum dose 325 mg/day) is permitted.

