7. Arterial or venous thromboembolic event, including but not limited to myocardial infarction, transient ischemic attack, cerebrovascular accident, or unstable angina, within 6 months prior to enrollment.

8. Uncontrolled or poorly controlled hypertension (> 160 mmHg systolic or > 100 mmHg diastolic for > 4 weeks) despite standard medical management.
9. Gastrointestinal perforation, and/or fistula, or risk factors for perforation within 6 months prior to enrollment.
10. Grade 3 or 4 gastrointestinal bleeding within 3 months prior to enrollment.
11. History of autoimmune disease, including but not limited to systemic lupus erythematosus, rheumatoid arthritis, inflammatory bowel disease, vascular thrombosis associated with antiphospholipid syndrome, Wegener's granulomatosis, Sjögren's syndrome, Bell's palsy, Guillain-Barré syndrome, multiple sclerosis, autoimmune thyroid disease, vasculitis, or glomerulonephritis.

Note: Patients with a history of autoimmune hypothyroidism on a stable dose of thyroid replacement hormone are eligible. Patients with controlled type 1 diabetes mellitus on a stable insulin regimen are eligible.

12. History of idiopathic pulmonary fibrosis, pneumonitis (including drug-induced), organizing pneumonia (i.e., bronchiolitis obliterans, cryptogenic organizing pneumonia, etc.), or evidence of active pneumonitis on screening chest CT scan.
13. Hemoptysis (defined as bright red blood or \geq ½ teaspoon) within 2 months prior to Cycle 1 Day 1 or with radiographic evidence of intratumor cavitation or radiologically documented evidence of major blood vessel invasion or encasement by cancer.
14. Serious or non-healing wound, ulcer, or bone fracture within 28 days prior to Cycle 1 Day 1.
15. Undergone major surgery within 28 days prior to Cycle 1 Day 1, or minor surgery/subcutaneous venous access device placement within 7 days prior to Cycle 1 Day 1, or has elective or planned major surgery to be performed during the course of the clinical trial.
16. Known clinically significant liver disease, including cirrhosis at a level of Child-Pugh B or worse, cirrhosis (any degree) with a history of hepatic encephalopathy or clinically meaningful ascites resulting from cirrhosis (defined as ascites from cirrhosis requiring diuretics or paracentesis), fatty liver, and inherited liver disease.

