5.3.2 Atezolizumab

Concomitant therapy includes any prescription medications or over the counter preparations used by a patient between the 7 days preceding the screening evaluation and the treatment discontinuation visit.

Patients who experience infusion-associated symptoms may be treated symptomatically with acetaminophen, ibuprofen, diphenhydramine, and/or cimetidine or another H2 receptor antagonist, as per standard practice (for sites outside the United States, equivalent medications may be substituted per local practice). Serious infusion associated events manifested by dyspnea, hypotension, wheezing, bronchospasm, tachycardia, reduced oxygen saturation, or respiratory distress should be managed with supportive therapies as clinically indicated (*e.g.*, supplemental oxygen and β_2 -adrenergic agonists).

Systemic corticosteroids and TNF α inhibitors may attenuate potential beneficial immunologic effects of treatment with atezolizumab but may be administered at the discretion of the treating physician. If feasible, alternatives to corticosteroids should be considered. Premedication may be administered for Cycles ≥ 2 at the discretion of the treating physician. The use of inhaled corticosteroids and mineralocorticoids (*e.g.*, fludrocortisone) for patients with orthostatic hypotension or adrenocortical insufficiency is allowed. Megestrol administered as appetite stimulant is acceptable while the patient is enrolled in the study.

Patients who use oral contraceptives, hormone-replacement therapy, prophylactic or therapeutic anticoagulation therapy (such as low-molecular-weight heparin or warfarin at a stable dose level), or other allowed maintenance therapy should continue their use. Females of reproductive potential should use highly effective means of contraception.

It is strongly recommended that:

- Traditional herbal medicines not be administered because the ingredients of many herbal medicines are not fully studied and their use may result in unanticipated drug-drug interactions that may cause, or confound assessment of, toxicity.
- The use of a RANKL inhibitor (denosumab) be discontinued during the study; this agent could potentially alter the activity and the safety of atezolizumab.

Patients are not allowed to receive immunostimulatory agents, including, but not limited to, IFN- α , IFN- γ , or IL-2, during the entire study. These agents, in combination with atezolizumab, could potentially increase the risk for autoimmune conditions.

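### The no-recent-bleeding condition for anticoagulated patients covers heparin and LMWH only, so a patient on an oral anticoagulant with a recent minor bleed, or varices outside exclusion 16, remains eligible (low priority, cheap to fix)

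*Combined protocol and SAP*

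**What the plan says.** The note under inclusion criterion 8 (section 3.1) has three parts.

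- **Who may enter on full-dose anticoagulation.** Patients who have been on a stable dose for at least 14 days "of oral anticoagulant or low molecular weight heparin (LMWH").
- **Warfarin.** The INR must not exceed 3.0. No other condition is attached to warfarin.
- **Bleeding.** "For heparin and LMWH there should be no active bleeding (that is, no bleeding within 14 days prior to first dose of protocol therapy"). The same sentence goes on to rule out a "or pathological condition present that carries a high risk of bleeding (for example, tumor involving major vessels or known varices").

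Section 5.3.2 treats the drugs alike once the patient is on study. It says patients using "prophylactic or therapeutic anticoagulation therapy (such as low-molecular-weight heparin or warfarin at a stable dose level") should continue it, and it adds no bleeding condition. An oral anticoagulant would therefore be taken alongside ramucirumab.

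**The concern.** The note regards a bleed in the last 14 days, or a high-risk lesion such as varices, as reason enough to keep a patient out of the trial. It applies that only to heparin and LMWH, although it admits oral anticoagulants on the same footing. Read literally, two patients with the same bleeding history differ in eligibility for an anti-VEGFR-2 antibody because of the anticoagulant they take.

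The wording looks more like an oversight than a decision. The bleeding sentence names heparin, which the opening sentence does not list, and leaves out oral anticoagulants, which it does list. No reason for exempting oral agents is given. For warfarin, the general INR limit of 1.5 is relaxed to 3.0 with no bleeding condition in exchange.

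This is a matter of patient safety at entry. It does not bear on the response rate estimate or on the test of it.

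**Working it through.** The plan states no figure on this point, so there is none to reproduce. The check compares the texts and then gives an illustrative range for the number of patients.

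**Step 1. What the other criteria already catch, whatever the anticoagulant**

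| Condition | Criterion | Bars an oral-anticoagulant patient? |
|---|---|---|
| CNS bleeding, grade 1 or higher | Exclusion 4, within the brain-metastasis criterion: "CNS hemorrhage based on pretreatment MRI or IV contrast CT scan" | Yes |
| Severe GI bleeding | Exclusion 10: "Grade 3 or 4 gastrointestinal bleeding within 3 months prior to enrollment" | Yes |
| Hemoptysis as defined, within 2 months | Exclusion 13 | Yes |
| Cavitation or major-vessel involvement | Exclusion 13: "with radiographic evidence of intratumor cavitation or radiologically documented evidence of major blood vessel invasion or encasement by cancer" | Yes |
| Serious or non-healing wound or ulcer within 28 days | Exclusion 14 | Yes |
| Varices with significant liver disease | Exclusion 16: "Known clinically significant liver disease, including cirrhosis at a level of Child-Pugh B or worse" | Yes, where the liver disease qualifies |
| GI bleeding of grade 1-2, within 14 days | None | No |
| Bleeding at another site, such as epistaxis or hematuria, within 14 days | None | No |
| Known varices outside exclusion 16 | None (varices are named only in the item 8 note) | No |

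The last three rows are the gap. Tumor involving major vessels, the note's other example, is not part of it, because exclusion 13 applies to everyone.

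**Step 2. The same patient, with one of those three conditions, by drug**

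- LMWH: not eligible.
- Warfarin: eligible if INR is at most 3.0, which is 3.0 / 1.5 = 2 times the item 8a limit.
- Other oral agent: eligible if INR is at most 1.5 and PTT/aPTT is below 1.5 x ULN (items 8a and 8b).

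**Step 3. How many patients**

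The documents give neither the share of patients on a full-dose oral anticoagulant nor the share of those with a residual condition. Both ranges below are assumptions for illustration.

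- *a*, on a full-dose oral anticoagulant: 5% to 15%.
- *b*, residual condition among those: 5% to 20%.
- From the documents: planned total 21 (section 14.2); patients still to be accrued at Amendment 3, 9 (section 1.6.1).

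Joint share *p* = *a* x *b*:

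- Low: 0.05 x 0.05 = 0.0025 (0.25%).
- High: 0.15 x 0.20 = 0.03 (3%).

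Expected affected patients, *n* x *p*:

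- Of 21: 21 x 0.0025 = 0.0525 to 21 x 0.03 = 0.63.
- Of 9: 9 x 0.0025 = 0.0225 to 9 x 0.03 = 0.27.

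Chance of at least one among the 9, 1 - (1 - *p*)^9:

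- Low: 1 - 0.9975^9 = 0.022, about 2%.
- High: 1 - 0.97^9 = 0.240, about 24%.

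**The case against.** **A scheme that differs by drug may be deliberate.** Warfarin has its own numeric control, other oral agents stay under items 8a and 8b, and heparin and LMWH get a clinical condition. An INR cap is itself a control on bleeding risk. This is possible, and the documents do not settle it. But coagulation tests measure the intensity of anticoagulation; they do not reveal a recent nosebleed, hematuria or varices, which are what the note treats as disqualifying on LMWH. If the exemption is intended, it should be stated with its reason.

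**The contrast is softer than it looks.** The note words the stable dose and the warfarin INR as obligations and the bleeding condition as a recommendation. That is fair, although a condition placed among the inclusion criteria will normally be applied as a requirement.

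**Further criteria shrink the group.** Platelets of at least 100,000 and hemoglobin of at least 9.0 (item 7) remove some patients with substantial blood loss or portal hypertension. Exclusion 6 bars chronic antiplatelet and NSAID use apart from daily aspirin. Exclusion 9 bars recent GI perforation, fistula or risk factors for perforation. Exclusions 7 and 21 bar recent thromboembolism and so reduce the number of anticoagulated patients. Exclusion 16 is broad enough that many patients with varices from liver disease would be caught. All of this stands. It makes the varices part narrow and leaves mainly recent minor bleeding, but it does not close the gap.

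**The investigator would not enroll such a patient.** Section 3.2 has no general exclusion at the investigator's discretion, and eligibility is confirmed against a checklist (section 4.1). The discretion in section 5.5 and the holds in section 6.1.7 act only after entry.

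**The numbers rest on assumptions.** They do. The upper figure of 24% needs one in five oral-anticoagulant users to have a residual condition. The range shows only that the group is small and may not be empty. No harm is quantified either: entering with a recent minor bleed is not itself an adverse outcome.

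**Conclusion.** The concern holds on the literal text. The 14-day no-bleeding and high-bleeding-risk condition does not reach oral anticoagulants, and no other criterion bars a recent grade 1-2 GI bleed, a recent bleed at sites such as the nose or urinary tract, or varices outside exclusion 16.

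Its size is small. Even at the top of the assumed ranges, fewer than one affected patient is expected among 21. The text comparison needs no assumption beyond reading the bleeding sentence as a requirement; the patient counts depend entirely on the two assumed shares. This is a low-priority safety clarification, worth making because it is cheap, with no consequence for the efficacy analysis.

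**What to change.** In the item 8 note, replace the words that limit the bleeding sentence to heparin and LMWH with *for all patients on full-dose anticoagulation (oral, heparin or LMWH)*. Keep the warfarin INR cap of 3.0 as an additional condition, and change the matching line of the eligibility checklist. If the sponsor's clinicians do intend oral anticoagulants to be exempt, say so in the note and give the reason.

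The cost is one phrase in section 3.1 and one checklist line. The downside is an occasional extra screen failure.

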3.2 Exclusion Criteria

1. Treatment with cyclophosphamide, azathioprine, methotrexate, thalidomide, and anti-tumor necrosis factor [anti-TNF] agents) within 2 weeks prior to Cycle 1, Day 1.

Note: Patients who have received acute, low-dose, systemic immunosuppressant medications (e.g., a one-time dose of dexamethasone for nausea or premedication for contrast dye allergy) are eligible. The use of inhaled corticosteroids for chronic obstructive pulmonary disease (COPD) and mineralocorticoids (e.g., fludrocortisone) for patients with orthostatic hypotension or adrenocortical insufficiency is allowed.

2. A history of other malignancy ≤ 3 years previous with the exception of patients with a negligible risk of metastasis or death and with expected curative outcome (such as adequately treated carcinoma in situ of the cervix, basal or squamous cell skin cancer, localized prostate cancer treated surgically with curative intent, or ductal carcinoma in situ treated surgically with curative intent) or undergoing active surveillance per SOC management (e.g., Rai Stage 0 chronic lymphocytic leukemia, prostate cancer with Gleason score ≤ 6 and prostate-specific antigen (PSA ≤ 10 ng/mL, etc.).
3. Currently receiving any other investigational agents.
4. Symptomatic or untreated asymptomatic brain metastases. Patients with treated brain metastases are eligible if they are clinically stable with regard to neurologic function, off steroids after cranial irradiation (whole brain radiation therapy, focal radiation therapy, and stereotactic radiosurgery) ending at least 2 weeks prior to randomization, or after surgical resection performed at least 28 days prior to randomization. The patient may have no evidence of Grade ≥ 1 CNS hemorrhage based on pretreatment MRI or IV contrast CT scan (performed within 21 days before randomization).
5. A history of allergic reactions attributed to compounds of similar chemical or biologic composition to atezolizumab, ramucirumab, any other immune checkpoint blockade, chimeric or humanized antibodies, fusion proteins, or other agents used in the study.
6. Receiving chronic antiplatelet therapy, including aspirin, nonsteroidal anti-inflammatory drugs (NSAIDs, including ibuprofen, naproxen, and others), dipyridamole or clopidogrel, or similar agents. Once-daily aspirin use (maximum dose 325 mg/day) is permitted.
7. Arterial or venous thromboembolic event, including but not limited to myocardial infarction, transient ischemic attack, cerebrovascular accident, or unstable angina, within 6 months prior to enrollment.

8. Uncontrolled or poorly controlled hypertension (> 160 mmHg systolic or > 100 mmHg diastolic for > 4 weeks) despite standard medical management.
9. Gastrointestinal perforation, and/or fistula, or risk factors for perforation within 6 months prior to enrollment.
10. Grade 3 or 4 gastrointestinal bleeding within 3 months prior to enrollment.
11. History of autoimmune disease, including but not limited to systemic lupus erythematosus, rheumatoid arthritis, inflammatory bowel disease, vascular thrombosis associated with antiphospholipid syndrome, Wegener's granulomatosis, Sjögren's syndrome, Bell's palsy, Guillain-Barré syndrome, multiple sclerosis, autoimmune thyroid disease, vasculitis, or glomerulonephritis.

Note: Patients with a history of autoimmune hypothyroidism on a stable dose of thyroid replacement hormone are eligible. Patients with controlled type 1 diabetes mellitus on a stable insulin regimen are eligible.

12. History of idiopathic pulmonary fibrosis, pneumonitis (including drug-induced), organizing pneumonia (i.e., bronchiolitis obliterans, cryptogenic organizing pneumonia, etc.), or evidence of active pneumonitis on screening chest CT scan.
13. Hemoptysis (defined as bright red blood or \geq ½ teaspoon) within 2 months prior to Cycle 1 Day 1 or with radiographic evidence of intratumor cavitation or radiologically documented evidence of major blood vessel invasion or encasement by cancer.
14. Serious or non-healing wound, ulcer, or bone fracture within 28 days prior to Cycle 1 Day 1.
15. Undergone major surgery within 28 days prior to Cycle 1 Day 1, or minor surgery/subcutaneous venous access device placement within 7 days prior to Cycle 1 Day 1, or has elective or planned major surgery to be performed during the course of the clinical trial.
16. Known clinically significant liver disease, including cirrhosis at a level of Child-Pugh B or worse, cirrhosis (any degree) with a history of hepatic encephalopathy or clinically meaningful ascites resulting from cirrhosis (defined as ascites from cirrhosis requiring diuretics or paracentesis), fatty liver, and inherited liver disease.
17. Active hepatitis B virus (HBV) or hepatitis C virus (HCV) infection (defined as, HBV surface antigen (HBsAg) positive and HBV core antibody (HbcAb) positive with reflex positive HBV DNA. Note: Patients with past or resolved hepatitis B infection (defined as having a negative HBsAg test and a positive HbcAb test or treated HCV with negative HCV RNA are eligible).
18. Active tuberculosis.

19. Administration of a live, attenuated influenza vaccine within 4 weeks before Cycle 1 Day 1 or at any time during the study.
20. Severe infections within 2 weeks prior to Cycle 1 Day 1, including but not limited to hospitalization for complications of infection, bacteremia, or severe pneumonia. Received oral or intravenous (IV) antibiotics within 2 weeks prior to Cycle 1 Day 1. Note: Patients receiving prophylactic antibiotics (e.g., for prevention of a urinary tract infection or chronic obstructive pulmonary disease) are eligible.
21. History of deep venous thrombosis, pulmonary embolism, or any other significant thromboembolism (venous port or catheter thrombosis or superficial venous thrombosis are not considered “significant”) during the 3 months prior to Cycle 1 Day 1.
22. Pregnant and/or breastfeeding. Women of childbearing potential must have a negative serum pregnancy test within 7 days of study entry.
23. Known HIV-positivity.

3.3 Inclusion of Women and Minorities

Both men and women and members of all races and ethnic groups are eligible for this trial.

4.0 REGISTRATION PROCEDURES

Patients must not start any protocol intervention prior to registration through the Siteman Cancer Center.

The following steps must be taken before registering patients to this study:

1. Confirmation of patient eligibility
2. Registration of patient in the Siteman Cancer Center database
3. Assignment of unique patient number (UPN)

